We will conduct a three-group, between-subjects experiment to compare varying cigarillo warning formats: Surgeon General text-only, FDA-proposed text-only, and our developed pictorial cigarillo warning labels. This will be a single survey study.

Setting

Survey participants will complete the online survey in a location of their choosing.

Subjects Selection Criteria

Participants will be recruited by Kantar, a leading data and consulting company with access to 21 million respondents in the United States. Kantar has participated in survey programming and data collection for various social science and public health studies, including tobacco. They will recruit a total of 1,575 cigarillo users, including oversampling Black/African American cigarillo users, with an estimated total of 635 Black/African American and 647 White cigarillo users

Inclusion Criteria

- Age 21-35
- Current cigarillo users: used cigarillos at least one time per week in the past month
- Members of the Kantar Media panel

Exclusion Criteria

- Non-English speakers
- Non-current cigarillo users
- Not members of Kantar Media

Sample Size

- We estimate 1575 participants will be eligible to complete the survey.

Interventions and Interactions

Kantar will contact individuals to participate, who will complete an eligibility screener. Eligible participants will first complete measures of demographics and tobacco use behaviors. Next, participants will be randomized to one of three experimental conditions to complete six purchasing tasks (i.e., mock shopping trips). Participants will indicate their preferred brand and flavor of cigarillos.³² If their preferred brand of cigarillo is not one of the top four brands, we will ask them to select one of the available brands. The experimental stimuli will be placed on that branded packaging.

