We will ask participants the average amount of money they spend each week on tobacco products; they will receive that balance for each mock (i.e., hypothetical) shopping trip, as is standard for ETM studies.³³ We will ask participants to imagine they were shopping in a convenience store, and to view six items available for purchase: preferred cigarillo brand, cigarette product (menthol and non-menthol), e-cigarette product (three variations), oral nicotine pouches, non-alcoholic drink, and snack food. They will be instructed to make hypothetical purchases of tobacco products that they would use for the week. In each shopping trip, the price of cigarillos will increase while those of alternative products remain the same. In each trial, participants can choose any combination of tobacco and non-tobacco products to ‘buy’, as long as they stay within their experimental budget. Across six mock shopping trips, the price of one of their preferred cigarillo products will increase from \$0.25, 0.50, \$0.75, \$1.50, \$3.00, \$6.00, based on an average price of \$0.91 per cigarillo.³⁴ Cigarette price will remain constant at \$6.00 per pack (\$0.30 per cigarette), e-cigarettes will be priced at \$4 per e-liquid pod or \$6 for 30 ml e-

liquid or \$12 for disposable device, and oral nicotine will be priced at \$4.00. Food and drink will be priced at \$2 each. Cigarillos will be purchased as singles to generate demand curves (see Measures and Analysis Plan).. This models other ETM studies.³³

After completing the hypothetical purchase tasks, we will assess additional constructs from our conceptual model. First, we will assess cigarillo warning label recognition (a measure of attention). We will then show the cigarillo warning to participants from their assigned experimental condition and ask them to respond to items assessing negative affect, thinking about the warnings, and intentions to quit using cigarillos.

At the end of this experiment, participants will view a **debriefing** page, including an explanation of the purpose of the study, emphasizing that the study is not promoting the use of cigarillos or any tobacco product and will include links to cessation services and information about the harms of cigarillo use. Participants will be compensated with 100 points (~\$2 value) by Kantar. These points can be used in exchange for a variety of items, including gift cards. We will not collect any identifying information such as name or birthdate.

Outcome Measure

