The average total number of cigarillos purchased is the primary outcome.

We will assess secondary outcomes: average total amount (mg) of combusted and non-combusted tobacco purchased in the ETM.

In secondary analyses, we will also generate demand indices for cigarillos, including: demand intensity (consumption at the lowest cigarillo cost), demand elasticity (rate of change in demand for cigarillos), price of cigarillos resulting in maximum purchasing, the amount of money spent at the maximum purchasing price.

In exploratory analyses, we will assess cross-price elasticity measures, negative affect, cognitive elaboration (thinking about the warnings), intentions to quit using cigarillos, perceived message effectiveness, and warning recall/recognition, which is a measure of attention.

We will also measure several **covariates**: use of other tobacco products, cigarillo dependence, sexual orientation, race/ethnicity, socioeconomic status, sex, gender identity, and age.

Analytic Plan

This study will examine the impact of cigarillo warnings on purchasing behavior in a hypothetical shopping task using the online Experimental Tobacco Marketplace. The primary outcome is the average total amount of cigarillos “purchased” (hypothetical shopping task) compared across study conditions.

Baseline differences between participants (e.g., sex) across warning conditions will be examined using t-tests for continuous variables and χ^2 tests for categorical variables to evaluate randomization balance. The primary outcome, average total number of cigarillos purchased, will be modeled using random-effects linear regression models to account for the within-person correlation among the repeated measures represented by the six purchasing tasks. Warning condition will be included as a between-subjects fixed effect. Models will control for any variables that differ at baseline between conditions. We will also assess whether Black/African-American race moderates the effect of warning condition by including interaction terms between Black/African American race and warning condition. These same analyses will also be

conducted for our secondary outcomes for average total of mg combusted and non-combusted tobacco products.

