In secondary analyses, demand curves will be generated for each cigarillo warning condition in each of the ETM conditions using the exponential demand equation, $Q = Q_0 * 10^k(e^{-\alpha Q_0 C} - 1)$, where Q is the mg of nicotine purchased at a given price, Q_0 is peak demand consumption or intensity (typically occurring at the lowest price), k is a constant across all compared conditions, and alpha (α) is the rate of change in demand or elasticity.³⁵ To determine the extent to which pictorial warnings decrease cigarillo purchasing relative to the text-only warning conditions, the global fits of the demand curves for cigarillos from each condition will be compared using an extra-sum-of-squares F-test, which compares whether the fitted parameters (specifically, Q_0 and α) are significantly different across each curve. A significant difference in α would represent a difference in the essential value of the product, while a difference in Q_0 would indicate that purchasing was reduced in absolute terms but the underlying 'value' of the product was unchanged.^{36,37} Finally, each individual demand index will be compared across conditions using t-tests to determine if pictorial warnings affected specific indices of demand differentially. The number of cigarillos purchased is higher for text-only warnings compared to pictorial warnings at the same price, but demand overall will decrease as price increases.

Exploratory analyses will examine the effects of warning condition on other constructs in the conceptual model including negative affect, cognitive elaboration, behavioral intentions, and warning recall/recognition. Because these outcomes are measured only once after the completion of all six purchasing tasks, continuous outcomes will be modeled using standard linear regression modeling and categorical outcomes will be modeled using logistic and multinomial regression. All tests will be two-sided with a 0.05 significance level.

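### The race-by-warning interaction on raw cigarillo counts needs a named comparator, a variance that allows spread to differ by race, and a stated effect scale

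*Combined protocol and SAP*

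**What the plan says.** Under Outcome Measure, "The average total number of cigarillos purchased is the primary outcome". The Analytic Plan says that this outcome "will be modeled using random-effects linear regression models to account for the within-person correlation among the repeated measures" over the six shopping trips, with warning condition as a fixed effect. Moderation by race is assessed by "including interaction terms between Black/African American race and warning condition", and the same analyses are repeated for the secondary mg outcomes. The stated level is "All tests will be two-sided with a 0.05 significance level".

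The plan mentions no link function, transformation, count model, robust variance or race-specific variance. A single common variance is the default of such a model, but the plan does not state it. The reference group for the race term and the scale on which moderation is judged are also not given.

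Subjects Selection Criteria gives a total of 1,575 "with an estimated total of 635 Black/African American and 647 White cigarillo users". Under Interventions and Interactions, participants report their average weekly tobacco spend and "they will receive that balance for each mock (i.e., hypothetical) shopping trip".

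**The concern.** Each person's purchases are capped by their own budget. As an illustration, $20 buys at most 80 cigarillos at $0.25 and 3 at $6.00. Counts on such a scale often have a spread that rises with the mean. If spending differs by race, both mean and spread may differ by race. The budget rule makes this plausible; the documents do not show it.

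Two separate consequences would follow.

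- **Standard error.** A model with one common variance gives the wrong standard error for the interaction when the groups differ in both spread and size.
- **Scale.** A linear model on counts defines moderation as a difference in cigarillos. If a warning cuts purchases by the same percentage in both groups but the groups buy different volumes, the additive interaction is not zero.

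The study oversamples Black users, this interaction is the only race analysis the plan specifies, and the results are meant to inform rulemaking. A statement that a warning works differently by race should therefore say in what sense it does.

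**Working it through.** The documents give no power calculation, effect size, mean or SD, so there is no stated figure to reproduce. The results below are conditional on assumed ranges.

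**Inputs from the documents.** Total 1,575; 635 Black and 647 White; all non-Black 1,575 - 635 = 940; three conditions; two-sided 0.05.

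**Assumptions.** Equal allocation (no ratio is stated), complete data on six trips, SD ratio Black:other of 0.5 to 3, CV (SD divided by mean) of 0.75 to 1.5, and a common reduction of 0 to 30%.

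With complete data, the random-intercept interaction estimate and standard error equal those from ordinary least squares on person means. A fitted check gave 1.079 and 1.080 for the two interaction terms under both methods. The closed form below therefore applies.

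**1. Standard error with no warning effect, one contrast (pictorial versus one text arm)**

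Let n_B and n_O be the per-arm group sizes, and let the SDs be r (Black) and 1 (other).

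- True variance = 2 × (r²/n_B + 1/n_O)
- Model variance = 2 × [(n_B r² + n_O)/(n_B + n_O)] × (1/n_B + 1/n_O)
- Type I error = 2 × [1 - Φ(1.96 × model SE / true SE)]

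Black versus all others: n_B = 635/3 = 211.67 and n_O = 940/3 = 313.33. For r = 2:

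- True variance = 2 × (4/211.67 + 1/313.33) = 0.0442, so SE = 0.210.
- Pooled variance = (211.67 × 4 + 313.33)/525 = 2.210. Model variance = 2 × 2.210 × 0.00792 = 0.0350, so SE = 0.187.
- SE ratio = 0.187/0.210 = 0.890. Type I error = 2 × [1 - Φ(1.744)] = 8.1%.

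| SD ratio | 635 vs 940: model SE / true SE | Type I error | 635 vs 647: model SE / true SE | Type I error |
|---|---|---|---|---|
| 0.5 | 1.124 | 2.8% | 1.006 | 4.9% |
| 0.67 | 1.077 | 3.5% | 1.004 | 4.9% |
| 1 | 1.000 | 5.0% | 1.000 | 5.0% |
| 1.5 | 0.928 | 6.9% | 0.996 | 5.1% |
| 2 | 0.890 | 8.1% | 0.994 | 5.1% |
| 3 | 0.855 | 9.4% | 0.993 | 5.2% |

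A simulation for 635 versus 940 at ratio 2 (gamma-Poisson purchases over the six prices, person-effect CV 1, 1,500 runs) gave 8.9% for one contrast and 10.5% for the joint two-degree-of-freedom test.

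**2. Scale, with the same percentage reduction p in both groups**

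The additive interaction is p × (mean_Black - mean_other) in size. Take mean_other = 1, mean_Black = 2, p = 0.2, CV = 1, a reduction in the pictorial arm only, and SD proportional to the mean:

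- Interaction = 0.2 × (2 - 1) = 0.2.
- True variance = (1 + 0.8²) × (4/211.67 + 1/313.33) = 1.64 × 0.02209 = 0.0362, so SE = 0.190.
- Pooled variance over three arms = 2.210 × (1 + 1 + 0.64)/3 = 1.944. Model variance = 2 × 1.944 × 0.00792 = 0.0308, so SE = 0.1755.
- Chance of flagging = 1 - Φ((1.96 × 0.1755 - 0.2)/0.190) plus a 0.2% lower tail = about 23%.

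| Volume ratio (635 vs 940) | 20% cut, CV 1.5 to 1 |
|---|---|
| 0.5 | 7-14% |
| 0.8 | 4.0-4.8% |
| 1.2 | 5.5-6.1% |
| 1.5 | 9-12% |
| 2.0 | 14-23% |

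At volume ratio 2.0, a 10% cut gives 9-11% and a 30% cut gives 23-43%. With CV 0.75 the 20% and 30% figures rise to 34% and 64%. For 635 versus 647 at ratio 2.0, the 20% and 30% cuts give 9-16% and 16-32% (CV 1-1.5), so the scale issue does not depend on the comparator. For 635 versus 940, part of each figure is the standard-error effect from step 1, since SD here moves with the mean.

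**3. What each remedy does (same simulation, CV 1)**

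- Raw counts with robust standard errors and no effect in either group: 4-6% rejection.
- Robust standard errors alone, 635 versus 940, volume ratio 2, 30% common cut: 41% rejection, against 46% with the default (joint test). Robust variance corrects the error bars and does not change the scale.
- Ratio-scale interaction with robust variance, equal percentage effects: 4-7% rejection in every setting.

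**The case against.** The strongest reply is that the primary outcome is a count, so a difference in cigarillos averted is a legitimate moderation estimand. This stands. When percentages match and volumes differ, the absolute effects really do differ, so much of the flagging in step 2 is power for a true additive interaction. The argument is also symmetric: an equal absolute reduction would appear as moderation on a ratio scale. Nothing in the documents ranks one scale above the other.

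Three further objections also stand.

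- A reader might infer that a difference in purchase volume alone makes the error bars wrong. It does not: spread must differ and, for the interaction, group sizes must differ too. With 635 Black and 647 White participants the standard error is right to within 1%. Black versus all others is the natural reading of the race term, but the plan does not name the comparator.
- No volume or SD by race is given, and the common variance is inferred from silence. At modest volume ratios (0.8 to 1.2) with a 20% cut, flagging stays at about 4-6%.
- Moderation is an additional analysis, separate from the primary comparison of warning conditions.

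What survives is that the plan leaves comparator, variance and scale open where choosing them costs almost nothing.

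**Conclusion.** The point holds as a cheap improvement of modest severity.

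The additive raw-count scale follows directly from the text. If spread differs by race and the comparison is 635 versus 940, the default standard error gives a type I error of about 7-8% at SD ratios 1.5-2.0 and about 3-3.5% at 0.5-0.67. The direction depends on which group varies more. For 635 versus 647 there is no material error. If volumes differ, an equal percentage effect is flagged in about 6% to 23% of trials over volume ratios 1.2 to 2.0 (20% cut, CV 1-1.5), and the risk lies in how that result is read. These sizes rest on equal arms, complete data and assumed ratios.

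A reader might infer that the stated 5% level fails, or that the plan will produce false moderation findings. The documents support neither: they report no race difference in volume or spread, and an additive interaction detected when absolute effects differ is not a false positive.

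**What to change.** In the Analytic Plan:

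1. Name the comparator for the race term: Black versus all others, or Black versus White.
2. Use participant-clustered robust standard errors, or race-specific variances, for the race-by-condition terms.
3. Beside the additive interaction, report a ratio of rate ratios from a log-link GEE clustered on participant. A quasi-Poisson form also suits the continuous mg outcomes; a negative-binomial form would not.
4. State the scale, absolute or relative, of any moderation claim. The ratio scale need not be the sole decision rule.

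Cost: a few sentences of plan text and a few lines of code, with no new data. The downsides are slightly wider intervals if the variances are in fact equal, and two interaction estimates to explain.

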In exploratory analyses, to determine the extent to which each alternative product substituted for cigarillos, cross-price elasticities will be calculated as the slope of the regression line (B_1) fit to the log-transformed mean purchasing in mg of nicotine for each alternative tobacco product when offered at fixed prices (C) versus log-transformed cigarillo price (P): $\log C = B_0 + B_1 \log P$. Positive values indicate product substitution. We will use PRISM GraphPad Version 8.1.1 to generate the behavioral economics indices, demand curves, and cross-price elasticities. We will be able to determine if viewing a pictorial warning on a cigarillo resulted in substitution with another tobacco product without a pictorial warning, such as cigarettes or e-cigarettes, or a non-tobacco product, such as food or drink.

Every effort will be made to minimize the presence of missing data. Analyses will use all available data. Since missing data in a single item of a multi-item scale leads to a missing total, we will consider imputing both at the level of the item and scale total. Additionally, to evaluate the generalizability of our results, we will use t-tests and chi-squared tests to examine pairwise differences in characteristics between participants for whom we have complete data and those for whom we do not.

Human Subjects Protection

Subject Recruitment Methods

Kantar works with permission-based panels with 88 million respondents, including 21 million in the United States. Recruitment includes traditional advertising and through internal and external affiliate networks. Kantar uses a diverse set of sources to reduce panel bias. When recruiting participants into studies, Kantar engages in data validation to ensure quality respondents and

responses. Kantar will recruit participants, directly inviting them to participate in the experiment. Potential study participants will complete an eligibility screener for inclusion into the ETM study. Participants must be ages 21-34 and be current cigarillo users (use cigarillos at least one time per week for the past month). Further, because we are studying cigarillo warnings in the U.S., only those living in the U.S. are eligible. Kantar will also oversample for young adult Black/African American cigarillo users. Kantar oversamples by enrolling approximately 20% additional participants to the study.

Informed Consent

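### The secondary F-test on the demand curves makes no allowance for six correlated purchases per participant and does not say what is fitted; on either reading its 5% level is not held

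*Combined protocol and SAP*

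**What the plan says.** All references are to the Combined protocol and SAP. In the secondary analyses of the Analytic Plan, "demand curves will be generated for each cigarillo warning condition in each of the ETM conditions", and then "the global fits of the demand curves for cigarillos from each condition will be compared using an extra-sum-of-squares F-test". The parameters tested are Q0 and alpha, with k held constant. The stated purpose is to learn how far pictorial warnings lower purchasing relative to text-only warnings. A difference in alpha is to be read as a change in the product's value, and a difference in Q0 as less purchasing at unchanged value. On the level: "All tests will be two-sided with a 0.05 significance level".

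For the primary outcome, taken from the same six trips, the Analytic Plan uses random effects "to account for the within-person correlation among the repeated measures represented by the six purchasing tasks". No participant effect, clustering, bootstrap or permutation is named for the F-test. The data level of the curve fit is not given. Averages are mentioned only for the cross-price elasticities, where the line is "fit to the log-transformed mean purchasing in mg of nicotine for each alternative tobacco product". A later step adds that "each individual demand index will be compared across conditions using t-tests", without saying whether the indices are computed per participant.

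Interventions and Interactions asks for each person's own weekly tobacco spending, and "they will receive that balance for each mock (i.e., hypothetical) shopping trip". On size, Subjects Selection Criteria says: "They will recruit a total of 1,575 cigarillo users".

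**The concern.** An extra-sum-of-squares F-test takes its error term from residual scatter around the fitted curves, treated as independent and of equal variance. Neither condition is plausible here. A personal budget that applies on all six trips makes heavy buyers heavy throughout, which the plan itself accepts for the primary model. Scatter will also usually shrink as price rises and purchases approach zero.

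The two possible fitting levels fail differently. With individual purchases, 9,450 observations are treated as independent although only 1,575 people were randomised. With condition means, the error term is the lack of fit of 18 averages to the equation, which does not measure variation between participants.

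The plan attaches different meanings to a Q0 and an alpha difference. A false rejection would therefore be reported as a finding about how pictorial warnings work.

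**Working it through.** **1. The test and its nominal level.** Equal allocation is assumed: 1,575 / 3 = 525 per arm. With six prices there are 1,575 × 6 = 9,450 purchases. Separate curves have 3 × 2 = 6 parameters and a shared curve has 2, so

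F = [(SSE shared − SSE separate) / 4] / [SSE separate / residual df].

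Residual df are 9,450 − 6 = 9,444 for purchases and 18 − 6 = 12 for means. For two arms the df are (2, 6,296) and (2, 8). The upper 5% points of F(4, 9,444) and F(4, 12) return 0.0500, so the stated level is reproduced under the test's own assumptions.

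**2. Why correlation matters.** With equal variance and within-person correlation ρ, the variance of a person's six-trip total is (1 + 5ρ) times its value under independence. The variance of a contrast between prices is (1 − ρ) times. At ρ = 0.50 these factors are 3.5 and 0.5. The F-test uses a single error for both, so it understates one kind of uncertainty and overstates the other.

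**3. Simulation inputs.** From the documents: three arms, the total sample size, prices of $0.25 to $6.00, and the demand equation (read with the whole bracket in the exponent). Assumed, because the documents do not give them: median Q0 12; k 1.5 to 3; alpha 0.005 to 0.02; all SDs and correlations. There were 32 settings with 4,000 null trials each. A fixed mg-per-cigarillo conversion leaves F unchanged.

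**4. Individual purchases: null rejection of the joint test at nominal 5%.**

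| Data model | Correlation | Three arms | Two arms |
|---|---|---|---|
| Equal variance, additive person effect | 0 | 5.0% | 4.9% |
| | 0.05 | 7.1% | 6.5% |
| | 0.10 | 9.2% | 7.4% |
| | 0.25 | 16.5% | 12.6% |
| | 0.50 | 28.3% | 21.0% |
| | 0.75 | 35.7% | 24.5% |
| Same, whole counts cut at zero | 0.10 | 11.5% | 9.5% |
| | 0.14 | 14.5% | 11.3% |
| | 0.48 | 32.2% | 22.3% |
| | 0.72 | 38.9% | 26.8% |
| Person-specific curves, 20 settings | 0.23 to 0.73 | 20.2% to 45.4% | 15.3% to 31.1% |
| Unequal variance only | 0 | 11.0% to 11.3% | 8.8% to 9.2% |

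**5. Condition means, three-arm joint test.** Rejection was 0.0% with counts cut at zero, 0.9% to 39.1% with person-specific curves, and 7.4% to 70.8% with equal variance and correlation 0.05 to 0.75. The result depends on how closely the averages follow the equation, because that lack of fit is the error term.

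**6. Q0 and alpha tested separately (individual purchases, three arms).** Two person-specific settings, both with k = 2, noise SD 0.2 and variance falling with price, gave opposite patterns:
- SD log Q0 0.9, SD log alpha 0.4, alpha 0.005: Q0-only 40.8%, alpha-only 0.0%.
- SD log Q0 0.4, SD log alpha 0.9, alpha 0.02: Q0-only 5.4%, alpha-only 20.4%.

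No general direction can therefore be stated.

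**7. A second set with a different curve** (Q0 10, alpha 0.02, k 2), with person-specific curves in five settings. Three of them had a personal budget cap and whole counts. Mean correlation was 0.19 to 0.79. The joint test rejected in 23.5% to 45.1% on purchases and 11.4% to 62.6% on means. With the person-level draws made independently for each price, so that the correlation was zero, purchases still gave 14.6% to 21.8%. Correlation and unequal variance both contribute.

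**The case against.** Several points can be made on the plan's side.

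- **The inputs are assumed.** This stands. The percentages illustrate the problem and do not estimate it for this trial. The defect does not hang on one value, however: correlation 0.05 already gave 7.1%.
- **Correlation is not the only cause.** This also stands. With zero correlation, unequal variance alone gave 11.0% to 11.3%. It is a second reason why the test fails and does not rescue it.
- **The highest condition-means figure, 70.8%, comes from a model that allows negative purchases.** A re-run of that model gave about 39% negative values at $6.00 and 23% at $3.00, and cutting at zero took the rate to 0.0%. That figure should carry little weight. High rates do not need negative data, though: a person-specific setting with only positive purchases gave 62.6%.
- **For means, the rates span 5%.** This is so. For means, what is shown is loss of control in either direction, not inflation as such.
- **It is a secondary test, and other analyses cover the question.** The primary random-effects model is unaffected. The t-tests on demand indices, if done on per-participant indices, compare participants properly. Both limit the consequence. Neither corrects the F-test p-value, and the plan does not say that the indices are per participant.

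**Conclusion.** The concern holds. As written, the demand-curve F-test has no participant-level error and no stated fitting level. In these simulations it held 5% only with independent purchases of equal variance. If individual purchases are fitted, the joint test rejects too often: 7.1% at correlation 0.05, rising to 45.4% in the most heterogeneous setting. If condition means are fitted, the level can lie far below or far above 5%. Which of Q0 and alpha is over-called depends on the variance pattern and on how participants differ.

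These sizes rest on equal allocation and on assumed SDs, correlations, k and alpha, and other inputs could fall outside the ranges. A p-value below 0.05 from this test cannot be read at face value. The point is confined to one secondary test and should be fixed before analysis.

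**What to change.** State whether individual purchases or condition means are fitted, and keep the Prism curves as descriptive. Test Q0 and alpha separately, with p-values and intervals from a bootstrap that resamples whole participants within condition and refits the same curves. In four settings (2,000 trials each, 300 resamples) this rejected in 4.9% to 6.3% of null trials, with simulation error of about 0.5 points.

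Alternatives:
- **Participant-clustered sandwich variance using the full Hessian.** This rejected in 4.3% to 5.9% for the joint, Q0 and alpha tests over all 32 settings. The usual Gauss-Newton form is not enough, because the averaged curve departs from the equation. Its joint test reached 10.0% there and 10.5% in the second set.
- **Permutation of whole participants across conditions.** This is valid by construction as an overall test of no difference (3.5% to 7.0% in five settings of 400 trials, standard error about 1.1 points). It does not separate Q0 from alpha.
- **Nonlinear mixed-effects model with random log Q0 and log alpha.** This targets a typical participant's curve and not the average curve, so the plan must name which is intended.

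State also whether the t-tests use per-participant indices.

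The cost is SAP wording and a short script outside Prism, with no new data. Intervals will be wider and fewer curve differences will be significant. A mixed-effects fit, if chosen, may converge poorly when many purchases are zero.

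### The demand-curve plan reads any Q0 difference as an absolute reduction in purchasing, but in its own equation a lower Q0 at equal alpha can raise purchasing above the peak-spending price

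*Combined protocol and SAP*

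**What the plan says.** The secondary analyses in the Analytic Plan fit an exponential demand curve per warning condition, printed as "Q = Q_0 * 10^k(e^{-\alpha Q_0 C} - 1" followed by a closing bracket. In it, "Q_0 is peak demand consumption or intensity (typically occurring at the lowest price" and a closing bracket, "k is a constant across all compared conditions", and alpha "is the rate of change in demand or elasticity". An extra-sum-of-squares F-test compares Q0 and alpha between conditions, and its purpose is given as: "To determine the extent to which pictorial warnings decrease cigarillo purchasing relative to the text-only warning conditions".

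The plan then fixes how the result is to be read. An alpha difference means a change in essential value. For the other parameter, "a difference in Q_0 would indicate that purchasing was reduced in absolute terms but the underlying 'value' of the product was unchanged". The same paragraph states the expected pattern: "The number of cigarillos purchased is higher for text-only warnings compared to pictorial warnings at the same price".

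Under Interventions and Interactions, "the price of one of their preferred cigarillo products will increase from" $0.25 through $0.50, $0.75, $1.50 and $3.00 to $6.00. The Outcome Measure section also lists the price at the maximum and the money spent there as separate demand indices; I take these to be the peak-spending price and peak spending.

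**The concern.** The reading rule treats Q0 as if it moved the whole curve down while alpha held the shape. In this equation Q0 also multiplies price inside the exponent. Lowering Q0 alone therefore lowers the start of the curve and makes it decline more slowly with price, so two curves with equal alpha can cross.

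At stake is the sentence that would be written from a Q0-only result. It would be reported as purchasing reduced in absolute terms, possibly while the fitted curves show more cigarillos bought at the upper tested prices. Conversely, a warning that cut purchases by the same percentage at every price would not give a Q0-only result. It would show an alpha difference as well, which the plan reads as a change in essential value.

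**Working it through.** **Inputs.** From the documents: the equation, k common to all conditions, and the six prices. The documents give no value for Q0, alpha or k and no figure to reproduce. Everything numerical below is therefore an assumption shown over a range: Q0 of 20 against 16 (20% lower), k of 1.5 to 3, and alpha set so that spending peaks at a chosen price. Read literally, the printed line gives negative purchasing, because e^(-alpha·Q0·C) − 1 is negative. I take the whole k-bracket as the exponent of 10 and treat the print as a typesetting or extraction effect. The plan measures Q in mg of nicotine. If mg is a fixed multiple of the cigarillo count, alpha rescales and the percentages are unchanged.

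**Step 1: effect of Q0.** Write x = alpha·Q0·C.
- Price elasticity: d ln Q / d ln C = −k·ln(10)·x·e^(−x).
- Effect of Q0 at fixed price, alpha and k: d ln Q / d ln Q0 = 1 − k·ln(10)·x·e^(−x) = 1 + price elasticity.

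So a small cut in Q0 lowers Q where demand is inelastic and raises it where demand is elastic.

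**Step 2: spending.** C·Q = (x/alpha)·10^(k(e^(−x) − 1)). Q0 enters only through x, so peak spending depends on alpha and k alone, and the peak-spending price scales as 1/Q0.

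**Step 3: limits.** The largest value of x·e^(−x) is 1/e, so a peak exists only if k > e/ln(10) = 1.18. Below that, a lower Q0 lowers Q at every price. Above it, there is a second unit-elasticity price at 4.1, 8.3 and 17.7 times the peak price for k = 1.5, 2 and 3, beyond which the rise reverses. For a finite cut, the crossing lies between the old and new peak prices.

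**Step 4: one case in full.** k = 2 with the peak at $1.50 gives x = 0.2903 at the peak, so alpha = 0.2903/(20 × 1.50) = 0.00968. At $6.00:
- Q0 = 20: x = 1.161, Q = 20 × 10^(2(0.3131 − 1)) = 0.846.
- Q0 = 16: x = 0.929, Q = 16 × 10^(2(0.3950 − 1)) = 0.986, which is 16.6% higher.

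The curves cross at $1.68, between $1.50 and $1.875. Peak spending is 9.40 in both.

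**Step 5: change in purchases for a 20% lower Q0, equal alpha and k.**

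| k | Peak price | $0.25 | $0.50 | $0.75 | $1.50 | $3.00 | $6.00 | Six-price total |
|---|---|---|---|---|---|---|---|---|
| 2 | $0.91 | −14.3% | −9.1% | −4.4% | +6.6% | +16.2% | +9.8% | −7.7% |
| 2 | $1.50 | −16.5% | −13.2% | −10.0% | −1.7% | +9.9% | +16.6% | −10.4% |
| 2 | $3.00 | −18.2% | −16.5% | −14.8% | −10.0% | −1.7% | +9.9% | −13.2% |
| 2 | $6.00 | −19.1% | −18.2% | −17.4% | −14.8% | −10.0% | −1.7% | −15.4% |
| 3 | $0.91 | −14.8% | −9.8% | −5.0% | +8.4% | +28.1% | +40.9% | −7.7% |
| 3 | $1.50 | −16.9% | −13.8% | −10.7% | −1.9% | +13.4% | +33.5% | −10.5% |

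At k = 1.5 with the peak at $0.91, purchases rise at $1.50 and $3.00 (+4.2%, +4.7%) and fall again at $6.00 (−8.0%), which is the second reversal.

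The six-price total rises only when the peak is very low. At $0.25 it is up 3.3% for k = 2 and 5.9% for k = 3. At $0.35 it is level for k = 2 and up 1.2% for k = 3. By $0.50 it falls (−3.2% and −2.8%).

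**Step 6: the converse.** If Q falls to 0.8·Q at every price, alpha·Q0 must stay the same while Q0 becomes 0.8·Q0. Hence alpha becomes alpha/0.8 = 1.25·alpha. This holds for any k, Q0 and alpha.

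**The case against.** The plan defines Q0 as intensity, so its phrase about an absolute reduction could mean only that this level fell. It nowhere says the fall holds at every price, and a reader who infers that claim goes beyond the text. That stands as a point about wording. The rule is nevertheless unqualified, it serves a comparison whose stated purpose is to show decreased purchasing, and the same paragraph expects fewer purchases at the same price.

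The percentages can also mislead. With k = 2 and the peak at $1.50, the four lower prices lose 5.57 units in all, while $3.00 and $6.00 together gain 0.40; the total goes from 49.65 to 44.48. This stands. A reader might infer that total purchasing rises or that the primary result is undermined. The documents do not support that, since the primary analysis models cigarillos purchased over the six tasks directly and does not use Q0 or alpha.

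A reader might also take unchanged peak spending as contradicting the plan. It does not: it agrees with the plan's statement that value is unchanged when alpha is equal.

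Finally, curves are already to be generated per condition and each index compared by t-test, so a crossing could be noticed. But nothing in the plan asks for it to be reported or allows it to alter the stated reading. The sources cited for the rule are not available here. The argument rests on the plan's equation alone.

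**Conclusion.** The concern holds as a fault of interpretation confined to a secondary analysis. It is algebraic that the effect of Q0 at fixed alpha is 1 plus the price elasticity, and that a uniform 20% cut gives Q0 × 0.8 with alpha × 1.25. A Q0-only difference is therefore not the signature of an across-the-board reduction.

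It would be tempting to say that the plan's reading is false over the upper part of the price ladder. The documents do not support this as a flat statement, because they give no Q0, alpha or k. A crossing needs k above 1.18. For the assumed 20% cut with k = 2, it affects three tested prices if the peak is $0.91, two if it is $1.50, one if it is $3.00 and none if it is $6.00. The plan's sentence is then true at every tested price in the last case.

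The sentence also describes only a reduction, although the tests are two-sided and a Q0 difference could be an increase.

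**What to change.** Replace the reading rule in the Analytic Plan as follows.
- A Q0 difference, in either direction, is read only as a change in intensity at near-zero price. An alpha difference is read as a change in essential value.
- Any secondary-analysis statement that a warning reduces purchasing rests on between-condition differences in purchases at the six tested prices.
- Fitted curves are shown by condition, with any crossing price reported.
- The plan notes that a uniform proportional reduction is expected to lower Q0 and raise alpha together.

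The cost is a few sentences and one table of purchases by price and condition. The planned tasks already supply the data, and the primary analysis does not change.
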